2. METHODOLOGY

2.1 Design

SLICE is an investigator-initiated, phase III, prospective, multicenter, randomized (1:1), open-label with blind end-point evaluation (**PROBE**), parallel-group trial comparing the efficacy and safety of an active search for PE (intervention group) with usual care (control group) in patients with unexplained exacerbations of COPD who require hospital admission (ClinicalTrials.gov identifier NCT02238639).

2.2 Setting

Emergency, Respiratory and Internal Medicine Departments in 18 Spanish University Hospitals.

2.3 Study subjects

Inclusion criteria (Table 1)

Patients are required to fulfill the following inclusion criteria:

1. Confirmation of COPD according to SEPAR-ALT criteria: post-bronchodilator forced expiratory volume in one second (**FEV1**)/forced vital capacity (**FVC**) < 0.7.
2. Hospital admission because COPD exacerbation without initial clinical suspicion of PE in the Emergency Department (according by the Emergency Department physician evaluation).

Exclusion criteria (Table 2)

A patient will be excluded from the study if ANY of the following apply:

1. Contraindication to multidetector CT pulmonary angiography (allergy to intravenous contrast medium, or renal failure defined as a creatinine clearance less than 30 mL/min, according to the Cockroft-Gault formula [**appendix 1**]).
2. Refusal to give informed consent.
3. Pregnancy, or breast feeding.
4. Life expectancy less than 3 months.
5. Anticoagulant therapy at the time of hospital admission.
6. Diagnosis of pneumothorax, or pneumonia (fever [temperature >38°C two times at least 12 hours apart], and purulent sputum, and new infiltrate in chest X-ray) at the time of hospital admission.
7. Diagnosis of lower respiratory tract infection (fever [temperature >38°C two times at least 12 hours apart], or increased sputum volume and increased sputum purulence) at the time of hospital admission.
8. Indication of invasive mechanical ventilation at the time of hospital admission.
9. Participation in any other investigational drug or device study in the past four weeks.
10. Geographic inaccessibility that precludes follow-up.

2.4. Randomization

In a patient with unexplained exacerbations of COPD requiring hospital admission, randomization should occur in the first 24 hours after admission. The trial will use a computer-generated randomization scheme. Randomization will be stratified by center and, within the centers, performed in blocks of 4 and 6 to ensure balanced distribution of the management groups. Randomization will be performed centrally via the Internet (www.estudioslice.org), and management allocation will be concealed from all investigators.

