4.2 Investigators

Participating investigators will be responsible for enrollment of patients who meet the inclusion and none of the exclusion criteria, obtaining informed consent, and management of patients randomized to the intervention.

Participating investigators will not be allowed to manage patients randomized to usual care.

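### Centre-stratified blocks of only 4 and 6, printed in the protocol and SAP of an open-label trial, leave upcoming allocations partly predictable, although the current assignment is concealed

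*Protocol*

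**What the plan says.** - Protocol 2.4 (Randomization): "Randomization will be stratified by center" and, within centres, is "performed in blocks of 4 and 6 to ensure balanced distribution of the management groups". SAP 2.3 says the same. Neither document says whether the two sizes come in random order, or that they are withheld from sites.
- The same protocol section describes the safeguard: "Randomization will be performed centrally via the Internet (www.estudioslice.org), and management allocation will be concealed from all investigators".
- Protocol 2.1 (Design): "randomized (1:1), open-label with blind end-point evaluation".
- Protocol 4.2 (Investigators): "Participating investigators will be responsible for enrollment of patients who meet the inclusion and none of the exclusion criteria". They also obtain consent and manage patients in the intervention arm, but "Participating investigators will not be allowed to manage patients randomized to usual care".
- Protocol 2.2 (Setting): "Emergency, Respiratory and Internal Medicine Departments in 18 Spanish University Hospitals".

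**The concern.** Concealing the current assignment and making the next one unpredictable are two separate protections. The plan secures the first. The second is weaker, because allocations within a centre must balance every 4 or 6 patients and earlier arms become visible. An enroller knows which arm a past patient joined: an intervention patient stays in that investigator's care and a usual-care patient does not. The documents do not say that sites hold the protocol, but Protocol section 6 requires the trial to comply with it, so this is a fair inference.

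There is room to act on a guess. Randomization may take place at any time in the first 24 hours after admission, and some entry criteria are matters of judgement, such as life expectancy under 3 months. Under Protocol Table 1, initial suspicion of PE means that the attending Emergency Department physician has indicated a D-dimer or CT angiogram. Eligibility therefore depends partly on a discretionary request for the tests under study, and Emergency Departments are a trial setting.

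At stake is selection bias at entry. Intention-to-treat analysis and blinded adjudication operate after enrolment and cannot remove it. The centre-stratified results in SAP 3.5.2 and the descriptive baseline table by strategy in SAP 3.4 are not designed to detect it.

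**Working it through.** The plan states no predictability figure, so there is none to reproduce. The sample size is not affected by this point.

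**1. Inputs.** From the documents: 1:1 allocation, block sizes 4 and 6, strata by centre, 746 patients, 18 centres, target reduction 40% to 30%. Average centre size is 746 / 18 = 41.4, taken as 41. Assumed, because the documents are silent: the two sizes occur in random order with equal probability.

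**2. Exact results when the size of each block is known.** Enumerate all balanced sequences and always guess the arm with more places left, scoring ties as one half.

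| Block | Expected correct guesses | Rate | Expected certain allocations | Rate |
|---|---|---|---|---|
| 4 | 2.833 | 2.833/4 = 70.8% | 1.333 | 33.3% |
| 6 | 4.1 | 4.1/6 = 68.3% | 1.5 | 25.0% |
| Equal mix | 6.933 per 10 | 69.3% | 2.833 per 10 | 28.3% |

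**3. Order of sizes unknown.** This is a simulation of 41-patient centres. The guesser knows the sizes are 4 and 6, sees every earlier allocation, and updates the probability of each block size and position after each patient.

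- Best guess correct: 68.7%, against 50% by chance, an excess of about 19 points.
- Predictable with at least 75% probability: 47%.
- Certain: 5.3% to 5.8% across repeat runs.

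**4. What publishing the sizes adds.** A guesser who ignores block size and picks the arm with fewer patients so far is also right 68.7% of the time. Knowing the sizes therefore adds almost nothing to the average. It is what makes an allocation certain, or lets the guesser attach a high probability to it.

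**5. Incomplete history.** The same running-count guess, when only part of the centre's earlier allocations is seen:

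| Share of history seen | Correct |
|---|---|
| 100% | 68.7% |
| 90% | 61% |
| 75% | 57.7% |
| 50% | 54.8% |
| 25% | 52.7% |

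**6. Possible bias.** Let G be the share of correct guesses and d the average difference in 90-day risk between patients enrolled under opposite guesses. The arms then differ at baseline by (2G − 1) × d. With G = 0.687 the multiplier is 2 × 0.687 − 1 = 0.374. The documents give no value for d, so these are illustrations.

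- d = 2 points: 0.374 × 2 = 0.7 points.
- d = 5 points: 0.374 × 5 = 1.9 points.
- 20% of enrolments steerable between patients at 30% and 50% risk, so d = 0.20 × 20 = 4 points: 0.374 × 4 = 1.5 points.
- The same d = 4 with 75% of history seen: (2 × 0.577 − 1) × 4 = 0.6 points. With 50% seen: (2 × 0.548 − 1) × 4 = 0.4 points.

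These run from 0.4 to 1.9 points against the 10-point target. They are not bounds. The bias is zero if nobody acts on a guess, and it grows in proportion to d.

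**7. Larger blocks in random order.** Same simulation, sizes still known to the guesser:

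| Blocks | Best guess correct | Predictable at 75% or more | Certain | Mean arm imbalance in a centre |
|---|---|---|---|---|
| 4/6 | 68.7% | 47% | 5.3–5.8% | 1.03 patients |
| 6/8/10 | 65.8% | 26% | 1.7% | 1.17 patients |

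With 41 patients the smallest possible imbalance is 1.

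**The case against.** Permuted blocks of two sizes within centre, run from a central web system, are a conventional design. Choosing larger blocks trades predictability against balance in centres of about 41 patients. That stands, and it makes this an improvement to a reasonable scheme.

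The full-history figures are an upper limit. Each hospital recruits through three departments, and nothing says that one enroller follows every allocation in order. Step 5 shows how quickly the advantage shrinks when tracking is incomplete. This also stands.

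Entry is constrained by spirometry, by listed exclusions and by the short randomization window. The judgement about PE suspicion belongs to the Emergency Department physician, who need not be the enroller. This limits steering but does not exclude it.

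The remedy hardly moves the average. With 6/8/10 the guess rate falls only to 65.8%, and the d = 4 illustration falls from 1.5 to (2 × 0.658 − 1) × 4 = 1.3 points. That is correct, but it looks only at the mean. The confident predictions, on which someone would be more likely to act, nearly halve.

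Finally, it is late. Revision 05 dates from September 2018 and follows the last interim analysis, while Protocol section 5 expected enrolment from late 2014 in a trial of about four years. Most allocations had probably been made. New blocks cannot repair those, which is why the SAP check matters.

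**Conclusion.** Upcoming allocations are partly predictable. With complete tracking, guesses are right about 69% of the time, 47% of allocations are predictable with at least 75% probability, and 5 to 6% are certain. These figures assume 41 patients per centre and a random, equal mix of sizes. If the sizes followed an order known to sites, the certain share could reach 28%; the plan does not say which applies. The effect on the treatment comparison cannot be determined from the documents.

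A reader might go further in two ways, and the documents support neither. The first is that allocation concealment fails. Allocation is central, web-based and stated to be concealed, and nothing suggests that a site can see the assignment of the patient being entered or the list behind it. The second is that sites can predict two thirds of allocations because the sizes were published. Half of those correct guesses would arise by chance at a rate of 50%, and the average is the same for a guesser who does not know the sizes. Small centre-level blocks in an open-label trial are the cause; publication matters mainly at the confident end.

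The point is modest and cheap to act on. There is no evidence that steering took place.

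**What to change.** 1. Remove the block sizes from Protocol 2.4 and SAP 2.3 and hold them in a randomization specification closed to sites. State in the protocol only that block sizes vary and come in random order.
2. For any remaining allocations, have the central system draw from a wider set of larger blocks in random order, for example 6/8/10. Document the date of the change.
3. For allocations already made, add one descriptive analysis to the SAP. For each patient, compute the predicted probability of intervention from the earlier allocations at that centre, and tabulate baseline age and FEV1 by that probability. Without steering, no trend is expected.

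The cost is some protocol wording, a setting in the web system and one table from data already held. The downside is slightly looser balance within centres, about 1.17 against 1.03 patients on average in a centre of 41. Removing the sizes now does not help where sites already know them, so items 2 and 3 carry most of the value.

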2.5 Study procedures

All patients will receive standard clinical management (usual care) for their COPD exacerbation according to the clinician's preference and local standards.

Intervention group

Patients in the intervention group will have blood samples collected from an antecubital vein, and will undergo D-dimer testing within 12 hours after randomization. Cut-off levels for defining elevated D-dimer will be defined by the Department of Clinical Chemistry at each participating site. For patients with a negative D-dimer, a diagnosis of PE will be ruled out. For patients with a positive D-dimer, a contrast-enhanced, PE-protocol, multidetector CT will be performed. CT pulmonary angiography results will be categorized as positive for PE if an intraluminal filling defect is seen in (sub)segmental or more proximal branches, and will be considered negative if no filling defect is observed. Scans will be considered technically inadequate only if main or lobar pulmonary vessels are not visualized. Though not mandatory, the protocol suggests the use of complete lower limb compression ultrasonography (**CCUS**) to detect concomitant DVT for patients with isolated subsegmental PE.

If the diagnosis of PE is confirmed, patients will receive anticoagulant treatment according to guideline recommendations: parenteral anticoagulation (i.e.,

unfractionated heparin, low-molecular-weight heparin, or fondaparinux) overlapped and followed by vitamin K antagonists; or parenteral anticoagulation followed by dabigatran or edoxaban; or monotherapy with apixaban or rivaroxaban (19).

Control group

Patients in the control group will receive standard clinical management (usual care) for their COPD exacerbation according to the clinician's preference and local standards.

After hospital discharge, all patients (in the intervention and control arms) will be treated according to the national and international recommendations for the management of stable COPD (1, 2).

2.6 Criteria for termination of the trial

Premature termination of the trial may happen under the following conditions:

- Occurrence of unknown or increase of known adverse events that render the risk/benefit ratio unacceptable.
- Interim analysis indicates reason.
- An unacceptable high number of SAEs.
- Ethical justification.
- Recruitment rate is too low such that it is unrealistic to consider completion of the trial within an acceptable period of time.
- Decision of the authorities.

2.7 Definition of study end points

Efficacy

The primary efficacy end point is the composite of death from any cause, non-fatal (recurrent) symptomatic VTE, or readmission for COPD exacerbation within 90 days after enrollment.

Confirmation of **(recurrent) symptomatic PE** requires symptoms of PE and a new or an extension of a previous intraluminal-filling defect in (sub)segmental or more proximal branches on PE-protocol chest CT pulmonary angiography.

Confirmation of **(recurrent) symptomatic DVT** requires symptoms of DVT and the following criteria: 1) In the absence of previous DVT investigations at baseline, a non-compressible venous segment on ultrasonography; 2) if there were previous DVT investigations at baseline, abnormal lower limb CCUS where compression had been normal; or, if previously non-compressible, a substantial increase (≥ 4 mm) in diameter of the thrombus during full compression.

Secondary efficacy end points include:

- Death from any cause within 90 days after enrollment.
- Nonfatal (recurrent) symptomatic VTE within 90 days after enrollment.
- Readmission for exacerbation of COPD within 90 days after enrollment.
- Length of hospital stay.

Safety

The primary safety end point is major bleeding within 90 days after enrollment.

Major bleeding is defined according to the guidelines of the International Society of Thrombosis and Haemostasis (20), as acute clinically overt bleeding associated with one or more among the following: a decrease in hemoglobin of 2 g/dL or more, a transfusion of two or more units of packed red blood cells, bleeding that occurs in at least one of the following critical sites (intracranial, intraspinal, intraocular, pericardial, intraarticular, intramuscular with compartment syndrome or retroperitoneal), bleeding that is fatal (defined as a bleeding event that the central independent committee adjudicate as the primary cause of death or contributing directly to death) and bleeding that necessitates surgical intervention.

Secondary safety end points include:

- Clinically relevant non-major bleeding within 90 days after enrollment.
- Serious adverse events (**SAE**) within 90 days after enrollment.

A bleeding event is classified as a **clinically relevant non-major** bleeding event if it is overt (i.e., is symptomatic or visualized by examination) not meeting the criteria for major bleeding, requires medical attention or is associated with discomfort for the subject such as pain, or impairment of activities of daily life.

Adverse event (AE): any untoward medical occurrence in a patient or clinical investigation participants, which does not necessarily have to have a causal relationship with the study intervention. An AE can therefore be any unfavorable and unintended sign (including an abnormal laboratory finding), symptom or disease temporally associated with the use of the study medication/procedure, whether or not considered related to the study medication.

Adverse reaction (AR): all untoward and unintended responses to a medicinal product related to any dose. The phrase "responses to a medicinal product" means that a causal relationship between a study medication and an AE is at least a reasonable possibility, i.e., the relationship cannot be ruled out. All cases judged by either the reporting medically qualified professional or the sponsor as having a reasonable suspected causal relationship to the study medication/procedure qualify as adverse reactions.

Serious adverse event: an event that fulfils one or more of the following criteria:

- Fatal.
- Immediately life-threatening.
- Results in persistent or significant disability/incapacity.
- Requires or prolongs in-patient hospitalization.

- Is a congenital anomaly/birth defect.
- Any other reason representing a significant hazard comparable to the criteria mentioned above.

Serious adverse reaction (SAR): an adverse event (expected or unexpected) that is both serious and, in the opinion of the reporting investigator, believed with reasonable probability to be due to one of the study treatments, based on the information provided.

Suspected unexpected serious adverse reaction (SUSAR): a serious adverse reaction, the nature or severity of which is not consistent with the applicable product information (e.g. Investigator's Brochure for an unapproved investigational product or summary of product characteristics for an approved product).

A central independent adjudication committee whose members are unaware of management allocation will adjudicate all suspected study outcomes during the study period.

Causality and expectedness

The relationship of each adverse event to the trial intervention must be determined by a medically qualified individual according to the following definitions:

Related: The adverse event follows a reasonable temporal sequence from trial intervention. It cannot reasonably be attributed to any other cause.

Not Related: The adverse event is probably produced by the participant's clinical state or by other modes of therapy administered to the participant.

Procedures for recording AEs

All AEs occurring during the study observed by the investigator or reported by the participant, whether or not attributed to study intervention, will be recorded on the e-CRF.

The following information will be recorded: description, date of onset and end date, severity, assessment of relatedness to study intervention, other suspect drug or device and action taken. Follow-up information should be provided as necessary.

AEs considered related to the study intervention as judged by a medically qualified investigator or the sponsor will be followed until resolution or the event is considered stable. All related AEs that result in a participant's withdrawal from the study or are present at the end of the study, should be followed up until a satisfactory resolution occurs.

The relationship of AEs to the study intervention will be assessed by a medically qualified investigator. Any pregnancy occurring during the clinical study and the outcome of the pregnancy should be recorded and followed up for congenital abnormality or birth defect.

Reporting procedures for SAEs

All SAEs must be reported to the Steering Committee or designated organization within one working day of discovery or notification of the event.

The Steering Committee or designated organization will perform an initial check of the report, request any additional information. All SAE information must be recorded on an SAE forms and faxed to the Steering Committee or designated organization. Additional information received for a case (follow-up or corrections to the original case) need to be detailed on a new SAE form and faxed to the Steering Committee or designated organization.

It may be appropriate that some SAEs do not require immediate reporting, but this must be justified. Justification might be determined, for example, by admission to hospital, or prolongation of hospitalization, where this is to be expected in the underlying disease or condition.

Type and duration of follow-up of subjects after SAEs

SAEs will be followed until resolved or considered stable. All SAE case report forms will be included in the e-CRF and will trigger an alert at the Data and Safety Monitoring Board.

2.8 Surveillance and follow-up

The study requires the following scheduled visits (see Section 3. Study procedures for details): enrollment, 1 week, 1 month, and 3 months after randomization. Additional visits are performed if new symptoms and/or signs of VTE or bleeding occur during the study period or anytime it is deemed necessary by the investigator. Clinical examination, laboratory and diagnostic imaging are performed if the patient develops symptoms or signs suggestive of (recurrent) VTE.

2.9 Cost-effectiveness analysis

The study will calculate the incremental cost-effectiveness ratio (**ICER**) according to the following formula:

$$\frac{\text{Cost}_{\text{active strategy}} - \text{Cost}_{\text{usual care}}}{\text{Effectiveness}_{\text{active strategy}} - \text{Effectiveness}_{\text{usual care}}}$$

where $\text{Cost}_{\text{active strategy}}$ and $\text{Cost}_{\text{usual care}}$ represent costs associated with the active strategy and usual care, respectively; while $\text{Effectiveness}_{\text{active strategy}}$ and $\text{Effectiveness}_{\text{usual care}}$ represent the clinical consequences as quality-adjusted life year (**QALY**) in both arms.

2.10 Statistical plan

Statistical design

SLICE is an investigator-initiated, phase III, prospective, international, multicenter, randomized (1:1), open-label with blind end-point evaluation, parallel-group trial comparing the efficacy and safety of an active search for PE (intervention group) with usual care (control group) in patients with unexplained exacerbations of COPD who require hospital admission

Null and alternative hypotheses

The primary aim of the trial is to demonstrate superiority in the intent-to-treat analysis of an active search for PE over usual care with regard to primary end point as the composite of death from any cause, non-fatal (recurrent) symptomatic VTE, or readmission for COPD exacerbation within 90 days after enrollment (90daycomposite).

The null and alternative hypotheses are as follows:

$$H_0: 90\text{daycomposite}_{\text{intervention}} = 90\text{daycomposite}_{\text{control}}$$

$$H_1: 90\text{daycomposite}_{\text{intervention}} \neq 90\text{daycomposite}_{\text{control}}$$

Analyses

The intention-to-treat (**ITT**) analysis dataset will be the source of data for all analyses. This will include all randomized participants regardless of actual receipt or compliance with the intervention. Safety analyses will also be performed in the safety analysis set, which will consist of all participant who receive D-dimer testing. In addition, a per-protocol (**PP**) analysis of all patients randomized and managed without major protocol violations/ deviations will be carried out; this dataset will support sensitivity analyses to complement the primary ITT analyses.

Protocol deviations (minor) refer to incidents involving non-compliance with the protocol that are unlikely to have a significant impact on the

participant's rights, safety or welfare, or on data integrity. Examples of deviations include forgetting to complete a procedure at a specified visit or a patient receiving an inadequate management strategy.

Protocol violations (major) refer to more serious incidents involving non-compliance with the protocol that may result in significant effect on the participant's rights, safety, or welfare or data integrity. Protocol violations could result in the participant being excluded from the eligibility analysis and/or result in the participant being discontinued from the trial. Examples of violations include non-compliance with inclusion/exclusion criteria or inadequate risk classification.

Efficacy analyses

The primary ITT analyses will be carried out by the chi square test on proportions, or the Fisher exact test. In addition, the corresponding 95% on the relative risks will be presented.

Safety analyses

The secondary ITT analyses will be carried out by the chi square test on proportions, or the Fisher exact test. In addition, the corresponding 95% on the relative risks will be presented.

Patient accountability

Disposition of patients, patient status and patients excluded from ITT will be summarized by group (intervention and control). Descriptive statistics for primary reason for patient's withdrawal will be also presented by group (intervention and control) as well as a list of these patients sorted by group (intervention and control).

Drop-outs

Reasons for drop-outs in each group (intervention and control) will be displayed. A detailed list of drop-out patients will also be provided.

Baseline characteristics

Baseline characteristics will be tabulated and comparability / differences between the treatment groups will be examined by means of descriptive statistics.

Subgroup analysis

The following subgroup analyses will be carried out: age (<75 versus ≥ 75), sex (women versus men), COPD severity ($FEV_1 > 80\%$, $50\% \leq FEV_1 < 80\%$, $30\% \leq FEV_1 < 50\%$, and $FEV_1 < 30\%$), hospital size (<300 beds versus ≥ 300 beds) and season (autumn, winter, spring, summer).

Interim analysis

We will conduct an interim analysis after recruitment of 50% of the study population. To preserve an overall type I error rate of 0.05 for the entire trial, the O'Brien-Fleming type boundary (alpha of 0.005) will be used for early trial stoppage. Futility will be assessed with conditional power, an approach that quantifies the probability of rejecting the null hypothesis of no effect. Stopping rule for futility will be based on a conditional power less than 20%.

Handling of missing data

Missing data won't be replaced, and analysis will be made on all evaluable patients. If necessary, sensitivity analyses will be made on the primary and secondary end points using worst case and/or multiple imputations (see 3.5.3). Missing or incomplete data for survival analyses will be managed by censored data analyses.

Sample size

Previous studies have shown short-term rates of death, thromboembolic events, or readmission of approximately 40% at day 90 among patients who required hospital admission because of an exacerbation of COPD (21, 22). An estimated 355 participants will be needed in each trial group to detect a clinically important 10% absolute reduction in the primary outcome (i.e., from 40% to 30%) with 80% power at 5% significance level. The 10% reduction was based on consultation with primary and secondary care colleagues (general practitioners and pulmonologists) who considered a 10% reduction to be small but clinically important. Since an interim analysis showed that 3% of patients were lost to follow-up, the Steering Committee anticipated a 5% loss to follow-up. This inflated each study group to 373 patients, giving 746 patients in total.

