3.2 Missing data

Missing data won't be replaced, and analysis will be made on all evaluable patients. In addition, sensitivity analyses will be made on the primary and secondary end points using worst case and/or multiple imputations (see 3.5.3). Missing or incomplete data for survival analyses will be managed by censored data analyses.

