7. PROTOCOL DEVIATIONS

Category	Excluded from
Inclusion/exclusion criteria	
Informed consent not available/not done/declined	All
Anticoagulant therapy at the time of hospital admission	All
Other exclusion criteria violated	PPS
COPD not objectively confirmed	PPS
Management strategies	
Randomization more than 24 hours after admission	PPS
D-dimer testing more than 24 hours after randomization	PPS
Missing CT pulmonary angiogram in patients with a positive D-dimer (intervention group)	PPS
End points	
Missing data on primary end points	PPS
Missing data on secondary end points	PPS

PPS: leading to the exclusion from the per-protocol population analysis.

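### Protocol 2.10 allows a randomized patient to be discontinued from the trial for a major violation, and neither document requires outcome follow-up to day 90 afterwards

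*Protocol*

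**What the plan says.** Protocol 2.10 (Analyses) defines the ITT dataset as the source for all analyses: "This will include all randomized participants regardless of actual receipt or compliance with the intervention". It limits the per-protocol set to patients without major violations or deviations and gives it a supporting role: "this dataset will support sensitivity analyses to complement the primary ITT analyses".

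The same subsection then sets out the consequences of a major violation: "Protocol violations could result in the participant being excluded from the eligibility analysis and/or result in the participant being discontinued from the trial". It adds: "Examples of violations include non-compliance with inclusion/exclusion criteria or inadequate risk classification". The term 'eligibility analysis' appears nowhere else and is not defined.

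On missing outcomes, SAP 3.2 does not replace missing values and says that "analysis will be made on all evaluable patients". Protocol 2.10 (Handling of missing data) has the same rule, and SAP 3.5.2 applies it to the principal analysis of the primary and secondary end points. SAP 4.2.2 keeps all randomized patients in the arm assigned. In SAP section 7, the row "Other exclusion criteria violated" leads to exclusion from the per-protocol set only.

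**The concern.** SAP section 7 works as intended only if patients with an eligibility violation have a known 90-day outcome, because it keeps them in the ITT comparison. The protocol clause allows a site to stop their participation. Outcomes are collected at trial visits and entered in the e-CRF at days 7, 30 and 90. Neither document separates stopping study procedures from stopping outcome collection. A site could therefore read "result in the participant being discontinued from the trial" as permission to make no further visits.

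The primary outcome would then be missing because of something found after randomization, in an open-label trial. Analysis cannot recover an outcome that was never collected.

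Late discovery of ineligibility is foreseeable. The fever component of the pneumonia and lower respiratory infection exclusions reads "fever [temperature >38°C two times at least 12 hours apart", while randomization is due within 24 hours of admission (Protocol 2.4). The second reading can therefore fall after randomization.

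**Working it through.** **1. The plan's own sample size.** Inputs from Protocol 2.10 (Sample size) and SAP 2.2: 40% against 30%, 80% power, 5% significance level. SAP 3.5.2 makes the test two-sided.

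- Pooled variance: n = [1.960·√(2·0.35·0.65) + 0.8416·√(0.40·0.60 + 0.30·0.70)]² / 0.10² = 355.9, so 356 per arm.
- Unpooled variance: n = (1.960 + 0.8416)²·(0.24 + 0.21) / 0.10² = 353.2, so 354 per arm.
- The stated 355 lies between the two and is reproduced to rounding.
- Inflation for 5% loss: 355 × 1.05 = 372.75, so 373 as stated; 355/0.95 = 373.7, so 374. The difference is immaterial.

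**2. How a patient can leave the comparison.**

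| Step | Source | Stated or inferred |
|---|---|---|
| A major violation may lead to discontinuation from the trial | Protocol 2.10 | Stated, as a possibility |
| Outcome collection stops at discontinuation | none | Inferred; nothing requires or forbids it |
| A missing outcome is not replaced; evaluable patients are analysed | Protocol 2.10; SAP 3.2, 3.5.2 | Stated |
| A patient with no recorded event and no day-90 status is left out of the primary test | none | Follows if the second step occurs |

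**3. Precision.** The documents give no number of violation-driven discontinuations. Assume that they come on top of the 5% loss, equally in both arms, and that all become non-evaluable. Evaluable patients per arm = 373·(1 − 0.05 − x):

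| Extra loss x | Evaluable per arm | Power, 40% vs 30% |
|---|---|---|
| 0% | 354.4 | 79.8% |
| 1% | 350.6 | 79.4% |
| 2% | 346.9 | 79.0% |
| 3% | 343.2 | 78.5% |
| 5% | 335.7 | 77.6% |

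**4. Bias.** Assumptions: true risk 40% in both arms (the plan's control rate, no effect); a fraction d of the intervention arm is removed and none of the control arm; those removed have event risk r.

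- Observed intervention risk: p = (0.40 − d·r)/(1 − d).
- Standard error: SE = √[p(1 − p)/(373(1 − d)) + 0.24/373].
- Chance of p < 0.05, with z = |p − 0.40|/SE: Φ(−1.96 + z) + Φ(−1.96 − z).

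| d | r | Observed risk | Shift (points) | z | Type I error |
|---|---|---|---|---|---|
| 2% | 60% | 39.6% | −0.4 | 0.113 | 5.1% |
| 2% | 80% | 39.2% | −0.8 | 0.227 | 5.6% |
| 5% | 60% | 38.9% | −1.1 | 0.290 | 6.0% |
| 5% | 80% | 37.9% | −2.1 | 0.582 | 9.0% |
| either | 40% | 40.0% | 0.0 | 0 | 5.0% |

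Here 2% to 5% of 373 is about 7 to 19 patients.

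**The case against.** A reader might infer that the clause itself ends 90-day follow-up and takes the patient out of the primary analysis, in direct contradiction of ITT. The documents do not say that. The clause says only that a violation could have this result. The ITT definition, SAP 4.2.2 and the per-protocol-only entry in SAP section 7 all point towards keeping the patient. An event recorded before discontinuation would still count. What stands is a gap: a permission with no follow-up rule attached. The explicit removals from the randomized set are elsewhere, in the SAP section 7 rows for missing consent and for anticoagulant therapy at admission, which exclude from all analyses.

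A reader might also infer that removal will be concentrated in the intervention arm, since only that arm has protocol D-dimer and CT. The support for this is weak:

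- Protocol 2.10 gives a forgotten procedure and an inadequate management strategy as examples of minor deviations, outside this clause. SAP section 7 does list late D-dimer and missing CT, but excludes those patients from the per-protocol set only.
- The pneumonia exclusion requires an infiltrate on chest X-ray together with fever and purulent sputum. Chest X-ray is a screening test in both arms, so an infiltrate seen only on CT does not meet the criterion.
- The timing of the fever readings is the same in both arms.

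The assumed rates can also be challenged. Both documents report 3% lost to follow-up at an interim analysis. Removing 5% of one arm is 18.65/746 = 2.5% of all patients. If the 3% includes discontinuations, nearly all of it would have to be violation-driven and in one arm.

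Finally, SAP 3.5.3 commits to worst-case and/or multiple-imputation analyses on the ITT population, and Protocol 2.10 requires reasons for drop-out by group, so an imbalance would be visible. This is a partial safeguard. The protocol makes the imputation analyses conditional on need, neither document specifies the method further, and neither analysis recovers uncollected outcomes. Following a related adverse event after withdrawal (Protocol 2.7) is not the same as following the primary end point.

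**Conclusion.** The point holds as a gap that should be closed. If a site uses the permission and stops collecting outcomes, a randomized patient without a recorded event drops out of the primary comparison, contrary to the all-randomized set and to SAP section 7.

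The bias cannot be sized from the documents. It is nil if removal is balanced between arms and unrelated to risk; then only precision is lost, and power stays at 77.6% or more with up to 5% extra loss. The shift of 0.4 to 2.1 points and the type I error of 5.1% to 9.0% rest wholly on assumed removal from the intervention arm alone, at above-average risk. The 9.0% is a pessimistic case, not an expectation. The reason to act is that the change is cheap and must be made before follow-up is lost.

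**What to change.** In Protocol 2.10, replace the clause on the consequences of violations with: *A protocol violation may affect membership of the per-protocol set but does not end outcome follow-up; every randomized patient is followed for the primary and safety end points to day 90 unless consent to follow-up is withdrawn.* State separately that stopping a study procedure is not the same as stopping outcome collection. Delete 'eligibility analysis' or define it.

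Cost: one paragraph of protocol wording and a note to sites. The sample size stays at 373 per arm and 746 in total. The only downside is completing visits that are already scheduled in a few ineligible patients.
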